8.1.2. Sensitivity Analyses

Randomized subjects who withdraw consent to participate in the study will not be replaced. The early termination rate is estimated to be 12%. To the extent possible, attempts will be made to minimize the amount of missing data through measures planned in the study conduct.

To investigate the possible implications of missing values in efficacy assessments, the number, timing, pattern, and reason for the missing value will be summarized. If there are missing values for the primary analysis, only available data will be analyzed and data obtained after rescue will not be excluded. To account for subjects for whom the post-baseline endpoint (ie, at the time when the last post-baseline double-blind assessment was performed) occurs at a time point before Week 24, a MMRM approach will be used as the primary method. It is assumed that the majority of the missing values will be one of the following:

- “Missing Completely at Random (MCAR)” (ie, probability of an observation being missing does not depend on observed or unobserved measurements) or
- “Missing at Random (MAR)” (ie, probability of an observation being missing depends only on observed measurements)

In such situations, likelihood-base methods like MMRM are appropriate.

The dropout patterns will be assessed by a Kaplan-Meier plot of time to discontinuation by treatment group to assess whether they differ between treatment groups.

For our primary analysis, it is assumed that a majority of the missing values will be MCAR or MAR. In such situations, likelihood-base methods like MMRM are appropriate and widely accepted in superiority trials (Little et al, 2002). This will be considered the primary analysis. Sensitivity analyses will be performed as:

1. Missing HbA1c data will be imputed via multiple imputations, following which the MMRM will be repeated on the complete datasets with results combined across complete datasets using standard MI techniques; HbA1c values collected after the start of rescue medication will not be considered missing.

2. Missing HbA1c data will be imputed via LOCF, following which the MMRM will be repeated; HbA1c values collected after the start of rescue medication will be considered missing.

3. HbA1c values collected after the start of rescue medication will be considered missing, and the MMRM analyses will be re-performed.

4. Missing HbA1c data will be imputed via multiple imputations, following which the MMRM will be repeated on the complete datasets with results combined across complete datasets using standard MI techniques; HbA1c values collected after the start of rescue medication will be considered missing.

For sensitivity analysis 1 and 4, data will be imputed in the framework of a pattern mixture model (PMM) with placebo-based pattern imputation for missing visits. The method described here is based on methodology described by Little and Yau (1996) and extended in a PharmaSUG paper by Ratitch and O’Kelly (2011). The concept for the imputation used here is that subjects who drop out of the study from the active treated arms will exhibit the same evolution of the disease under study as those subjects assigned to the placebo arm. It is assumed, as well, that subjects who discontinue from the placebo arm would have the same evolution of the disease as those subjects on the placebo arm who remained in the study. The three-step approach outlined below will be followed (Ratitch B and O’Kelly M, 2011):

1. Non-monotone (intermediate visits) missing data will be imputed first using the Monte Carlo Markov Chain method under the MAR assumption in all treatment arms (using the MCMC statement in PROC MI). Multiple chains option (CHAIN=MULTIPLE option in the MCMC statement of PROC MI) will be used. For the non-monotone imputation of the HbA1c missing data, a multivariate normal model will be used including variables for the HbA1c at baseline and all post-baseline visits within each treatment group.
2. After the non-monotone missing data have been imputed, the remaining monotone missing data will be imputed under the Missing Not at Random (MNAR) assumption that subjects who withdraw from the bexagliflozin group will have correlations with future (post-withdrawal) visits similar to subjects in the placebo group, adjusted for baseline covariates and observed outcomes prior to withdrawal. Monotone missing data of withdrawn subjects from the placebo group will be imputed under the MAR assumption and will follow the pattern of placebo completers. In other words, monotone missing values of the HbA1c will be imputed for all subjects who withdrew from the study (regardless of treatment group) using an imputation model at each time point estimated from subjects with available data in the placebo group only. A regression imputation model for the HbA1c at each time point t will include explanatory variables including

screening anti-diabetic treatment regimen [insulin treated or other], baseline eGFR [<45 or ≥ 45 mL/min/1.73m²), region and HbA1c at all previous time points, including baseline. Data from bexagliflozin group with time t data observed will not be used to impute time point t. Imputations will be performed using a sequence of regression-based imputations (using PROC MI statement MONOTONE REG) for each post-baseline time point as described in (Ratitch B and O'Kelly M, 2011).

3. Imputed data in each of the multiple imputed datasets will be analyzed using the same mixed model for repeated measures as in the primary analysis. The results from all imputed datasets will be combined using the Rubin's combination rule (PROC MIANALYZE).

The sample SAS codes can be found in Appendix 21.2.

The number of imputation will be determined using the method described by White, et.al., 2011. We will use Bodner's approximation to estimate the fraction of missing information (FMI) as the proportion of the incomplete cases in the data. Since the parameter of interest is the mean changes from baseline in HbA1c at Week 24 for bexagliflozin and placebo groups, FMI will be approximated using the proportion of subjects missing Week 24 values. As indicated by Bodner, this is a very conservative approach and will work with $FMI \leq 0.5$. The number of imputations m will be determined to provide sufficient level of reproducibility using formula:
 $m \geq 100 \times FMI$

as recommended by White. The Monte Carlo error of the P-value using m imputation datasets will be approximately 0.01 when the true P-value is 0.05, and 0.02 when the true P-value is 0.1.

At least 10 datasets will be imputed. We will examine the FMI estimated from the combined results. If it is much larger than our initial approximation, a considerable volatility is observed from the imputed datasets. In this case, we will increase the number of m using the estimated FMI.

For sensitivity analysis using LOCF, all observed data and the imputed values will be analyzed using MMRM model. Model will include terms for screening anti-diabetic treatment regimen (insulin treated or other), baseline eGFR (<45 or ≥ 45 mL/min/1.73m²), region, treatment, visit, treatment-by-visit, and the baseline HbA1c value as a fixed effect covariate. LS mean treatment differences between the bexagliflozin group and the placebo group will be estimated from the model with the corresponding p-values and their two-sided 95 % CIs presented.

Sensitivity analysis will be conducted for ITT Analysis Set. If > 5% subjects in either treatment arm had major protocol deviation that cause exclusion from PP analysis set, sensitivity analysis will be repeated for PP Analysis Set.

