6. GENERAL ASPECTS FOR STATISTICAL ANALYSIS

6.1. GENERAL METHODS

Statistical methodology and analyses are in accordance with the principles outlined by the ICH E9 guidelines. All statistical analyses will be conducted using SAS statistical software version 9.3 or higher.

Tables, listings and figures (TLFs) will be produced in accordance with the principles outlined by the ICH E3 guidelines. For most summary statistics, data will be analyzed by the following treatment groups: Bexagliflozin 20 mg and Placebo. All available data will be presented in the subject listings.

Data summaries will use descriptive statistics (number of subjects [n], mean, standard deviation [SD], Q1, median, Q3, minimum, and maximum) for continuous variables, and frequency and percentage of subjects for categorical and ordinal variables, unless otherwise specified.

Unless otherwise specified, all tests will be two-sided using a 0.05 level of significance. All confidence intervals (CIs) will be two-sided 95% CIs.

The analysis visit window will be assigned to data collection. One selected data point per visit will appear in summary tables and figures. Refer to section 6.4 for details. All visit assessment data will be included in shift tables and will appear in the subject listings.

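### The minimum number of imputations (100 x FMI, about 12 at the planned dropout) leaves avoidable seed noise of about 0.012 in a sensitivity p-value near 0.05; a larger fixed m would make it small

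*SAP*

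**What the plan says.** SAP section 8.1.2 describes placebo-based multiple imputation for HbA1c sensitivity analyses 1 and 4. On the number of imputations it says "The number of imputations m will be determined to provide sufficient level of reproducibility using formula", followed by m ≥ 100 × FMI. For the input, "FMI will be approximated using the proportion of subjects missing Week 24 values". The SAP regards this approximation as very conservative.

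It then gives the precision that the rule delivers: "The Monte Carlo error of the P-value using m imputation datasets will be approximately 0.01 when the true P-value is 0.05". For a p-value of 0.10 the corresponding figure is given as 0.02. A floor follows: "At least 10 datasets will be imputed". If the FMI estimated from the pooled results is well above the initial approximation, "In this case, we will increase the number of m using the estimated FMI".

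The same section gives the only planning figure for missing data: "The early termination rate is estimated to be 12" per cent. Sections 8.2.1.1 and 8.2.1.2 repeat sensitivity analysis 4 for body weight and systolic blood pressure. Section 6.1 sets the general standard: "all tests will be two-sided using a 0.05 level of significance".

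**The concern.** A multiple-imputation p-value depends on the random seed. The seed-to-seed standard deviation that the SAP accepts, about 0.01 at p = 0.05, is roughly one fifth of the threshold against which readers will judge the result. Because the minimum m scales with FMI, the noise does not shrink when more data are missing.

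Analyses 1 and 4 are the plan's only checks that depart from missing-at-random, which is the assumption behind the primary mixed model. Analysis 4 is also the only sensitivity analysis named for body weight and blood pressure. These two endpoints are tested in subsets (baseline BMI ≥ 25 kg/m², baseline SBP ≥ 130 mmHg), and the sample-size section (3.7) gives no power for them. A borderline sensitivity result there cannot be ruled out. If one occurred, its side of 0.05 could depend on the seed.

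**Working it through.** **Inputs.**
- Rule m ≥ 100 × FMI, floor 10 (SAP 8.1.2).
- FMI approximated by the proportion missing Week 24 (SAP 8.1.2).
- Early termination 12% (SAP 8.1.2), used here as a proxy for that proportion. This is an assumption, since missing Week 24 need not equal early termination. Minimum m = 100 × 0.12 = 12.
- Two-sided 0.05 level (SAP 6.1).
- Design difference 0.4%, SD 1.0%, 133 evaluable per arm (SAP 3.7).

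**The SAP's own figures.** The Monte Carlo variance of the pooled estimate is B/m, where B is the between-imputation variance and is about FMI times the total variance. Hence SD(z) = √(FMI/m) and SD(p) = 2·φ(z_p)·√(FMI/m). At m = 100 × FMI, √(FMI/m) = √(1/100) = 0.10 whatever the FMI.
- p = 0.05: 2 × φ(1.960) × 0.10 = 2 × 0.0584 × 0.10 = 0.0117.
- p = 0.10: 2 × φ(1.645) × 0.10 = 2 × 0.1031 × 0.10 = 0.0206.

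Both agree with the SAP's approximate 0.01 and 0.02. The floor of 10 binds only when FMI is below 0.10, and the error is then smaller than 0.0117 (0.0091 at FMI 0.06, m = 10).

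**If the true FMI is half the missing proportion.** FMI 0.06 with m = 12: 2 × 0.0584 × √(0.06/12) = 0.0083.

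**Simulation check.** The formula ignores the noise in the estimated between-imputation variance. Simulating Rubin's rules (100,000 runs, FMI 0.12, true p 0.05) gives somewhat more: SD 0.0139 at m = 12, with 95% of reported p-values between about 0.030 and 0.084. At m = 100 the SD is 0.0045 (0.042 to 0.060), and at m = 1,000 it is 0.0014 (0.047 to 0.053).

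**Chance that the seed changes the side of 0.05** (formula above; p = 0.04 is z = 2.054, p = 0.06 is z = 1.881):

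| FMI, m | SD(z) | SD(p) at 0.05 | true p 0.04 reported above 0.05 | true p 0.06 reported below 0.05 |
|---|---|---|---|---|
| 0.12, 12 | 0.100 | 0.0117 | 17% | 21% |
| 0.06, 12 | 0.071 | 0.0083 | 9% | 13% |
| 0.12, 100 | 0.035 | 0.0040 | 0.3% | 1.1% |
| 0.12, 1,000 | 0.011 | 0.0013 | about 0 | about 0 |

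The gain from m = 12 is √(100/12) = 2.9-fold at m = 100 and √(1,000/12) = 9.1-fold at m = 1,000. For FMI from 0.06 to 0.30, SD(p) is 0.0029 to 0.0064 at m = 100 and 0.0009 to 0.0020 at m = 1,000.

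**How often this would matter for HbA1c.** At the design effect, z = 0.4/√(2/133) = 3.26, p is about 0.001 and SD(p) is about 0.0004. Averaged over the sampling distribution of z, the chance that the seed moves p across 0.05 is about the density of z at 1.96 times the mean absolute seed shift: φ(3.26 − 1.96) × 0.10 × √(2/π) = 0.171 × 0.080 = 1.4%. If placebo-based imputation diluted the effect by 12% with 150 per arm (an assumption), z = 0.352/√(2/150) = 3.05 and the chance is φ(1.09) × 0.080 = 1.8%.

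**The case against.** The strongest defence is that nothing here is hidden or wrong. The SAP gives the rule, its published basis and the resulting error, and the calculation above only adds a digit. The rule is a lower bound, so 12 is a planning minimum and not a setting. Analysis 4 treats post-rescue values as missing, so its m would probably be higher (20% missing gives m = 20), although the error at the minimum stays 0.0117. The imputation analyses decide no test: the primary test and the hierarchy rest on the mixed model fitted to observed data, and the SAP sets no pass mark for the sensitivity analyses. All of this stands, and it makes the point minor.

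Three stronger readings are tempting, and the documents do not support them.
- A reader might infer that a larger m removes the noise for nothing. The noise falls as 1/√m, so some remains at any finite m, and there is computing to pay for.
- A reader might infer that raising m after pooling is a choice steered by the results. The trigger is the estimated FMI, not the p-value or the effect, and the step can only reduce Monte Carlo error. What can fairly be said is that no threshold is given for triggering it, and that an FMI estimated from 12 imputations is imprecise. With 11 degrees of freedom, a true 0.12 gives a between-imputation share of 0.12 × 3.82/11 = 0.042 to 0.12 × 21.9/11 = 0.239. Dividing each by itself plus 0.88 gives estimates of roughly 0.05 to 0.21.
- A reader might infer that no seed is specified. The SAS code is in Attachment 4, which was not available for this review, and the seed may be there.

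**Conclusion.** The point holds as a cheap improvement, not as an error. At the minimum m, the seed contributes a standard deviation of about 0.012 to a sensitivity p-value near 0.05 when the true FMI equals the missing proportion, and about 0.008 when it is half. A true p of 0.04 or 0.06 would then change sides for about 17% or 21% of seeds, or 9% or 13% in the second case. These are conditional figures. At the HbA1c design effect the noise is about 0.0004, and the overall chance of a seed-driven crossing is 1% to 2%. For body weight and blood pressure the documents give no effect assumptions, so whether their results would lie near 0.05 is unknown. The value m = 12 rests on using the 12% early-termination estimate for missing Week 24 values.

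**What to change.** In SAP section 8.1.2, replace the 100 × FMI minimum and the floor of 10 with one fixed m for all imputation analyses, including those for body weight and systolic blood pressure. At least 100 captures most of the gain; 1,000 makes seed-driven changes of side negligible even at p = 0.04 or 0.06. The step that raises m then becomes unnecessary and can be deleted. Confirm that the seed is stated in the SAS code attachment, and add it if it is not.

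The cost is SAP wording and some extra computing time for about 300 subjects and three post-baseline visits. No extra subjects, visits or data are needed.

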8.1.3. Subgroups

Both descriptive and model comparison for the primary analysis will be repeated by subgroups. The nominal p-value will be presented without adjustment to the multiple comparisons. They are not used for inferential purpose. The subgroups include:

- Age (<65 years or ≥65 years)
- Gender (male or female)
- Race (3 largest race groups or other)
- Baseline HbA1c (7.0% to 8.5% or 8.6% to 10.5%)
- Screening anti-diabetic treatment regimen (insulin treated or other)
- Baseline eGFR (30-44 mL/min/1.73m² or 45-59 mL/min/1.73m²)
- Region (North America, EU, or Asia)

8.2. SECONDARY EFFICACY ENDPOINT(S) AND ANALYSES

The key secondary efficacy endpoints include:

- Change from baseline to week 24 in body weight in subjects with baseline body mass index (BMI) ≥ 25 kg/m²
- Change from baseline to week 24 in SBP in subjects with baseline SBP ≥ 130 mmHg from baseline
- Change in HbA1c in subjects with eGFR 45 to 59 mL/min/1.73 m² at week 24
- Change in HbA1c in subjects with eGFR 30 to 44 mL/min/1.73 m² at week 24

The exploratory efficacy endpoints include:

- Change in HbA1c over time in all subjects
- Proportion of subjects who reach target HbA1c of <7% over time
- Changes in fasting plasma glucose (FPG) over time
- Proportion of ≥ 5% reduction of body weight in subjects with baseline BMI ≥25 kg/m² at week 24
- Change in body weight in all subjects over time

- Changes in SBP and diastolic BP over time in all subjects
- UACR categories at week 24 in all subjects and in subjects with baseline macroalbuminuria (UACR ≥ 300)

8.2.1. Key secondary efficacy endpoints and analyses

The primary superiority test on lowering of HbA1c at week 24 from baseline for bexagliflozin when compared to placebo will be conducted at 0.05 significance level. If it is significant, the hierarchical testing strategy will be followed to preserve experiment-wide type I error of 0.05. The key secondary efficacy end points will be tested in the order:

1. Superiority test of the change in body weight in subjects with baseline BMI ≥ 25 kg/m² at week 24 in the bexagliflozin group compared to the placebo group
2. Superiority test of the change in systolic blood pressure (SBP) over time in subjects with SBP ≥ 130 mmHg in the bexagliflozin group compared to the placebo group
3. Superiority test of the change in HbA1c at week 24 in subjects with eGFR 45 to 59 mL/min/1.73m² in the bexagliflozin group compared to the placebo group
4. Superiority test of the change in HbA1c at week 24 in subjects with eGFR 30 to 44 mL/min/1.73m² in the bexagliflozin group compared to the placebo group

These key secondary endpoints will only be tested sequentially when significant treatment differences are established for the primary efficacy endpoint in the comparisons between the bexagliflozin and placebo groups.

Analysis for key secondary endpoints will be based on the ITT Analysis Set and repeated for the PP Analysis Set.

8.2.1.1. Change in body weight from baseline to week 24 in subjects with a BMI ≥ 25 kg/m²

This will be tested if the change from baseline body weight is significantly different between bexagliflozin and placebo groups based on ITT analysis set for subject with a baseline BMI ≥ 25 kg/m². The comparison of change in body weight between randomized treatments at week 24 will be carried out using similar MMRM ANCOVA model stated in section 8.1.1. Treatment, visit, treatment-by-visit, region, baseline HbA1c level as continuous variable, screening anti-diabetic treatment regimen (insulin treated or other), baseline eGFR (<45 or ≥ 45 mL/min/1.73m²) will be applied as fixed effects. Corresponding baseline weight value will be used as additional covariate. Treatment comparison p-values and difference at week 24 will be estimated from the

model, with the two-sided 95 % CIs of the treatment difference also presented. If the primary hypothesis is not significant, the nominal p-value will not be used for inferential purposes. The most conservative sensitivity analysis, sensitivity analysis #4 in section 8.1.2, multiple imputations with values after rescue medication considered as missing, will be repeated in ITT analysis set.

8.2.1.2. Change in SBP from baseline to week 24 in subjects with baseline systolic blood pressure \geq 130 mmHg

This will be tested if the primary and the first key secondary efficacy endpoints are significant. Change from baseline in sitting SBP at week 24 will be analyzed using the same MMRM ANCOVA model stated in section 8.1.1. The corresponding baseline SBP value will be used as additional covariate. Treatment comparison p-values and difference at week 24 will be estimated from the model, with the two-sided 95 % CIs of the treatment difference also presented. The most conservative sensitivity analysis, sensitivity analysis #4 in section 8.1.2, multiple imputations with values after rescue medication considered as missing, will be repeated in ITT analysis set.

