3.2.2 Run-in Period

All eligible subjects will enter a one-week single blind, placebo run-in period to allow for diabetes education and optimization of compliance with diet and exercise recommendations. Qualified subjects will continue their pre-screening regimen for glycemic control (including OHAs and/or insulin) and will be instructed to take the run-in medication once daily for 7 and up to 9 days intended to familiarize subjects with trial procedures and to identify and reject subjects at high risk for non-compliance. During the run-in period, subjects will receive diet and exercise counseling and instructions on contacting the clinic in the event of hypoglycemia, hyperglycemia, or symptoms that may suggest ketoacidosis. Subjects will be trained to use the glucometer and record any events in the glycemic control diary. Adjustment of treatment for hypertension or dyslipidemia will not be permitted during the run-in period. If a change in treatment is required to appropriately manage dyslipidemia during the screening period, the subject may re-enter the screening as a new subject after the clinical condition and treatment regimen have not changed for at least 30 days. When re-screening, a new subject number will be assigned and all screening activities and assessments will be performed. Adjustment for anti-diabetic medication during the screening and run-in period is not permitted. Re-screening after adjustment for anti-diabetic medication is not recommended as it takes 12 weeks to establish an HbA1c stable baseline.

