5.6 Concomitant Therapy

During the course of the study investigators will manage glucose, blood pressure, lipid levels, and anemia according to local or regional standard of care guidance documents for the management of T2DM and other comorbidity or disease as issued by the relevant professional bodies (e.g. ADA, the National Kidney Foundation, etc.). Subjects should be provided access to all additional therapies and interventions during the course of the study if these are clinically indicated and approved by local competent authorities.

Subjects will be allowed to take medications or medicinal supplements prescribed to manage non-diabetic medical conditions during the study. Any concurrent medication or supplemental treatment of other, non-diabetes medical conditions should be continued at a stable dose and frequency for the entire study duration unless there is clinical reason to change the dose or frequency.

Blood pressure medications should not be altered during the screening period and the first 12 weeks of the main treatment period unless it is medically necessary to do so. If a change in treatment is required to appropriately manage anemia, or dyslipidemia during the screening period, the subject may re-enter the screening after the clinical condition and treatment regimen have not changed for at least 30 days. If it is medically necessary to alter blood pressure medications during the first 12 weeks of the treatment period to mitigate symptomatic hypotension, new diuretic medications should not be initiated and the dose and frequency of existing diuretic medications should not be increased. Changes to the dose or frequency of anti-hypertensive and diuretic medications must be recorded in the concomitant medications log.

Subjects who do not meet protocol-specified glycemic targets at specified time points during the study may receive rescue medication at the discretion of the investigator during the study. Anti-diabetic therapies prescribed to subjects for the purpose of treating hyperglycemia for more than 2 weeks will be considered rescue medications ([Section 5.2.4 Rescue Medications for Hyperglycemia](#)).

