3.10. STUDY PROCEDURES AND FLOWCHART

The activities that must be performed at each clinic visit listed below are presented in Table 1.

Table 1 Schedule of Events

Procedure	Screening	Run-in	Treatment						Follow-up
	V1	V2	V3	V4	V5	V6	V7	V8	V9
Time to Randomization	3 days -3 weeks to V2	-1	0	2	6	12	18	24	26
Informed Consent	X								
Screening for I/E Criteria	X		X						
Medical History	X								
Diet and Exercise Counseling		X							
Physical Examination			X						
Abbreviated Physical Examination	X					X		X	X
Weight	X		X		X	X		X	X
Vital Signs	X		X		X	X		X	X
Electrocardiography	X							X	
Diary and Glucometer Record Review			X	X	X	X	X	X	X
Dispensing Run-in Drug		X							
Randomization			X						
Dispensing Investigational Product			X			X			
Adverse Events & DKA Assessments		X	X	X	X	X	X	X	X
Concomitant Medication Assessments		X	X	X	X	X	X	X	X
Hematology	X		X		X	X		X	X
Serum Chemistry and Electrolytes	X		X		X	X		X	X
Glycemic Control	X		X		X	X		X	X
Serum Lipids	X		X			X		X	X
Urinalysis	X		X		X	X		X	X
UACR	X		X					X	X
Urine Pregnancy Test (WOCBP)	X		X		X	X		X	X
Population PK sampling					X	X			

A visit window of ± 3 days is allowed for all visits except Visit 3. V3 is the day of randomization and the basis for the visit window.

The study staff will contact each subject prior to a scheduled clinic visit to confirm the time of the visit and to remind the subject of proper fasting practice. A subject must be queried to assess compliance with a minimum of 8 hours fast prior to blood draw to ensure the FPG and triglycerides values can be accurately determined. If a subject has not fasted for a minimal of 8 h, the subject must return as soon as can be arranged (within 1 week) to provide a specimen after proper fasting.

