6.2. KEY DEFINITIONS

6.2.1. Baseline Values

For safety endpoints, baseline is defined as the last non-missing measurement prior to the first dose of double-blind IP. For baseline demographics and efficacy endpoints, baseline is defined as the last non-missing value before the randomization date. These endpoints include HbA1c values, sitting SBP, height, body weight, BMI, FPG, eGFR, and UACR.

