8.1.1. Primary Efficacy Analysis

Let $\mu_{\text{Bexagliflozin}}$ and μ_{PBO} represent the mean changes from baseline in HbA1c at Week 24 for bexagliflozin and placebo arms, respectively. The following hypotheses will be tested:

$$H_0: \mu_{\text{Bexagliflozin}} = \mu_{\text{PBO}} \text{ versus } H_1: \mu_{\text{Bexagliflozin}} \neq \mu_{\text{PBO}}$$

This hypothesis will be tested based on ITT analysis set using all observed data and a mixed model repeated measures (MMRM) approach. Treatment, visit, treatment-by-visit, region, screening anti-diabetic treatment regimen (insulin treated or other), baseline eGFR (<45 or ≥ 45 mL/min/1.73m²) will be applied as fixed effects. Baseline HbA1c will be used as covariate. The analysis will evaluate the mean change from baseline in HbA1c over the 24-week double-blind treatment period. An unstructured covariance will be used to model the within-subject correlation. The Kenward-Roger approximation will be used to estimate denominator degrees of freedom. If the model with the unstructured covariance structure does not converge, an autoregressive (1) covariance structure will be used. HbA1c values obtained after the start of rescue medication will not be excluded from the analysis.

Based on the MMRM model, the treatment and treatment-by-visit interaction terms allow for comparisons of the treatment groups at each visit. Least squares (LS) mean treatment differences between the bexagliflozin group and the placebo group at week 24 will be estimated from the model with the corresponding p-values and their two-sided 95 % CIs presented. Sample SAS code will be provided in Appendix 21.2.

Descriptive statistics (n, mean, Q1, median, Q3, SD, minimum, and maximum) will be reported by treatment group and visit, along with the least squares means, differences between LS means, a 2-sided 95% confidence interval for each difference, p-values from the model effects. In addition, the LS means with standard errors of the change from baseline over time and difference between treatment groups with 95% will be presented graphically for the ITT Analysis Set.

For supportive analyses, the primary efficacy endpoint will be analyzed with observed available data using the PP analysis set in a similar manner as above. LS means over time will also be presented graphically.

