9.5. VITAL SIGNS

Vital signs will be measured at the screening visit, baseline visit (Week 0), and at weeks 6, 12, 24, and 26. Measurements of vital signs will include measurement of supine, sitting and standing blood pressure (BP) measurements, and heart rate. Only the BP measured in the sitting position will be used to determine eligibility. Orthostatic systolic and diastolic BP will be calculated as supine measurement - standing measurement.

For BP, pulse rate, and respiration rate, observed values and change from baseline will be summarized by treatment group and visit using descriptive statistics (n, mean and median, SD, Q1, Q3, minimum, and maximum). BP summary will include supine, sitting, standing and orthostatic BP. Safety analysis set will be used for table summary. Subjects vital sign measurements, including scheduled and unscheduled visits, will be listed.

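### The key secondary SBP model adjusts for only one of two pre-treatment sitting SBP readings; adding the other, once the baseline visit is settled, is nearly free precision on a test that gates both eGFR HbA1c tests

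*SAP*

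**What the plan says.** **Model.** SAP 8.2.1.2 carries the primary model over to subjects with baseline SBP of at least 130 mmHg: "Change from baseline in sitting SBP at week 24 will be analyzed using the same MMRM ANCOVA model stated in section 8.1.1". It then adds one term: "The corresponding baseline SBP value will be used as additional covariate". The carried-over model (SAP 8.1.1) already has region, screening regimen (insulin or other) and baseline eGFR group as fixed effects, and "Baseline HbA1c will be used as covariate". Baseline SBP is therefore the only SBP covariate, but not the only baseline covariate.

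**Measurement.** SAP 9.5: "Vital signs will be measured at the screening visit, baseline visit (Week 0), and at weeks 6, 12, 24, and 26". Two of these visits precede study drug. Protocol 6.9 prescribes the same seated procedure at each. Screening is 3 to 21 days before run-in and run-in lasts 7 to 9 days, so the two readings are 10 to 30 days apart.

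**Background treatment.** Protocol 4.2 (criterion 6) requires stable antihypertensive doses for at least 30 days before randomization. Protocol 3.2.2: "Adjustment of treatment for hypertension or dyslipidemia will not be permitted during the run-in period". Protocol 5.6: "Blood pressure medications should not be altered during the screening period and the first 12 weeks" of treatment, with an exception for medical necessity.

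**Baseline definition.** SAP 6.2.1, which names sitting SBP: "For baseline demographics and efficacy endpoints, baseline is defined as the last non-missing value before the randomization date". SAP 3.10: "V3 is the day of randomization and the basis for the visit window". The schedule has no vital signs at V2.

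**Testing order.** SAP 8.2.1 places SBP second among the key secondary tests, after body weight and before HbA1c in eGFR 45–59 and then eGFR 30–44.

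**The concern.** A single clinic SBP is a noisy measure of a person's usual pressure. A second reading, taken by the same procedure under background treatment meant to be unchanged, carries further information on usual pressure and so may help predict the week-24 value. It is already collected and the plan does not use it in this model.

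The test concerned uses only part of the 300 subjects, no power is stated for it, and a non-significant result closes both HbA1c tests by eGFR group. Avoidable residual variance here therefore affects more than the SBP result.

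**Working it through.** **1. The plan's own figure.** For HbA1c with a difference of 0.4, SD 1.0, two-sided 5% and 90% power: n = 2(1.960 + 1.282)²/0.4² = 131.4, so 132 per arm by the normal formula. The t-test gives 132.3, so 133. Power at 133 is 90.1%. The stated 133 reproduces. It concerns the primary test only; the documents contain no counterpart for SBP, so every SBP input below is an assumption.

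**2. Gain under equal correlations.** Let ρ be the correlation between any two of V1, V3 and week-24 SBP. Relative residual variance is 1 − ρ² with one reading and 1 − 2ρ²/(1 + ρ) with two. Their ratio is 1 − (ρ/(1 + ρ))². New power = Φ((1.960 + z_power)/√ratio − 1.960).

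| ρ | variance ratio | power if 80% before | power if 60% before |
|---|---|---|---|
| 0.3 | 0.947 | 82.1% | 62.4% |
| 0.5 | 0.889 | 84.4% | 65.1% |
| 0.7 | 0.830 | 86.7% | 68.0% |

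Under normality, selecting on the baseline reading does not change this ratio. A simulation that also applied the 170 mmHg eligibility ceiling gave about 0.90 at ρ = 0.5.

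**3. The same in mmHg, with and without true change.** Assume between-person SD 13, visit-to-visit SD 11, 75 subjects per arm in the subset, 12% loss (66 evaluable) and a 4 mmHg effect.

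- Total variance = 169 + 121 = 290; reliability r = 169/290 = 0.583.
- One reading: 290(1 − r²) = 191.5 (SD 13.8). Two readings: 290(1 − 2r²/(1 + r)) = 165.5 (SD 12.9). The cut is 13.6% and power goes from 38% to 43%.
- Now add 10 mmHg SD of true 24-week change: 291.5 against 265.5. The cut is 26/291.5 = 8.9% and power goes from 27% to 29%.
- With 13/8 mmHg and the same added change, the residual variances are 210.4 and 190.9 (cut 9.3%) and power goes from about 35% to 38%.

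**4. Unequal correlations, V3 as baseline.** The ratio is 1 − p², where p = (r₁ − r₁₂r₃)/√((1 − r₁₂²)(1 − r₃²)). Here r₁₂ is V1–V3, r₃ is V3–week 24 and r₁ is V1–week 24. Take r₁₂ = 0.7 and r₃ = 0.5:

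- r₁ = 0.50: ratio 0.941 (80% power becomes 82.3%).
- r₁ = 0.45: ratio 0.974 (81.0%).
- r₁ = 0.35: ratio 1.000 (no gain).

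If V1 is the baseline, the added reading is V3. The last set then gives p = (0.5 − 0.7 × 0.35)/√(0.8775 × 0.51) = 0.381 and a ratio of 0.855. The strong-decay case removes the gain only when V3 is already the baseline.

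**5. The V1/V3 mean as replacement covariate.** The outcome is change from one reading. At 13/11 mmHg, before selection:

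- Var(week 24 − V3) = 2 × 121 = 242.
- Covariance with the mean = −121/2 = −60.5.
- Var(mean) = 169 + 60.5 = 229.5.
- Residual variance = 242 − 60.5²/229.5 = 226.

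Against 191.5 under the existing covariate, this is about 18% worse, because the baseline noise in the change score is no longer adjusted out.

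**6. Effect on the gated tests.** At the minimum of 135 subjects in an eGFR group less 12%, 59.4 per arm remain. With the plan's 0.4 and SD 1.0, power is about 58%. Treating the tests as independent, 2 to 3 extra points at SBP add at most 0.58 × 2 to 0.58 × 3, or about 1 to 2 points, to the chance of success on one eGFR test.

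**The case against.** The strongest objection is that nothing here is wrong. Adjusting for one pre-treatment value is a standard analysis with correct type I error, and using the last value before treatment agrees with Protocol 9.4. That stands: this is an efficiency point only. A reader might infer that the test is biased or that alpha control is damaged; nothing in the documents supports that.

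The size is also uncertain. Gains of 3 to 8 points appear only when no true change over 24 weeks is assumed. Antihypertensives are restricted only through week 12, and even then may be altered if medically necessary, so a weaker link to week 24 is plausible. This stands too, and lowers the realistic figure. The zero-gain case is less likely than it looks: it needs correlation to fall to 0.7 within 10 to 30 days yet only to 0.5 by week 24. If the early drop is mostly visit noise, a second reading still helps somewhat.

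A reader might also infer that selection at 130 mmHg makes the loss worse. By step 2 it does not.

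Finally, the advice to add V1 could be empty. Read literally, SAP 6.2.1 makes V1 the baseline already, since V3 is the randomization date. SAP 7.3 says only prior to randomization, and SAP 9.5 calls week 0 the baseline visit, so V3 was probably meant. Either way exactly one reading is unused, but the definition must be settled before the fix can name it.

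**Conclusion.** The point holds as a low-priority improvement. One of two pre-treatment sitting SBP readings is left out of a test that gates two others, and using it would leave the estimand, the subset and the type I error unchanged.

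On assumed equal correlations of 0.3 to 0.7, residual variance falls by about 5% to 17%. Allowing further true change over 24 weeks, about 2 to 3 power points is realistic; with V3 as baseline and strong decay of correlation, the gain is close to zero. These figures rest wholly on assumed SBP parameters. A reader might take the upper end as a demonstrated loss of power, but the documents contain no SBP inputs from which to show one.

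The ambiguity about which visit supplies baseline SBP is in the text itself and needs resolving whether or not the covariate is added.

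**What to change.** Before unblinding:

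1. In SAP 6.2.1, name the visit that supplies baseline SBP, and reconcile this with SAP 7.3, SAP 9.5 and Protocol 9.4.
2. In SAP 8.2.1.2, keep that value for the 130 mmHg subset, the change score and the existing covariate. Add the other pre-treatment sitting SBP as a second continuous covariate.
3. Give a rule for a missing second reading that ignores treatment assignment, so that no subject leaves the model for lack of it.
4. Use the same covariates in the SBP version of sensitivity analysis 4, in both the imputation and the analysis model.
5. Do not replace the baseline covariate with the V1/V3 mean.

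The cost is a few SAP sentences, matching program code and one degree of freedom. No new data are needed.
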